2.3 Sample size determination

The primary aim of the study is to demonstrate that patients in the "Drug target biomarker" group (Group 1) will have a higher response rate than the "No drug target biomarker" groups (Group 2 and 3)- see section 2.2 for trial diagram.

Using change in CDAI score from baseline (delta CDAI) as the primary outcome, a difference in delta CDAI between the two comparison groups of 10, with a Standard Deviation of 14.34. These are the values that were observed when analysing the difference in delta CDAI between biomarker positive and biomarker negative patients treated with MTX in the PEAC study. Although PEAC patients were not treated with Abatacept, this comparison is expected to be even more in favour of the biomarker positive group using Abatacept together with MTX. Thus, basing the power calculation on the PEAC observed difference is a conservative assumption.

With these assumptions, 90 patients would be needed to detect a significant difference of 10 in delta CDAI with 90% power. Since this would only be for Group 1 and Group 3 (45 patients each), a total of 180 patients would be sufficient for 90% power in the whole trial (Figure 1 Section 2.6). If we assume a 5% dropout rate and also account for an expected 5% of patients that have insufficient RNA for the Nano-string analysis (based on results from the STRAP trial), 200 patients in the whole trial would be sufficient to detect a significant difference (Group 1 vs Group 3) of 10 in delta CDAI with 90% power.

All power calculations were performed using the "twomeans" package in STATA, version SE 18.

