6.6.2 Handling of missing data

The missing values in primary outcome will be considered separately from other variables.

It is rare that the primary outcome is missing, but if so, the CDAI response at another visit will be used as the primary outcome. If a patient stops treatment before reaching visit 7 (when the primary endpoint is obtained) but CDAI response is available at visit 6, the CDAI at visit 6 will be used for the primary endpoint. When more than 5% of primary endpoint data is missing under other circumstances, Missing data for essential outcome variables and their subcomponents will be handled by multiple imputation by chained equation (MICE), incorporating longitudinal datapoints. Imputation will be performed five times and the mean (or median, if a particular variable is not Gaussian) result of imputation will be used to replace missing values. Imputed values will be checked for excessive variability across the five imputation runs assuming data are missing at random (MAR). Multiple imputations will be implemented using STATA (version 18 or higher). The performance of the imputations will be examined through the convergence and marginal distributions. Five imputations will be produced and the pooled results of the 5 analyses will be presented.

For questionnaires (SF-36, HAQ, EQ-5D-5L, ESS and FACIT fatigue), the database will produce the final scores. The missing component score values will be imputed using the same technique as describe above.

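### SAP 6.6.2 fixes five imputations with no Monte Carlo error criterion or rule for adding more, so a borderline primary p-value could turn on the random seed

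*SAP*

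**What the plan says.** Section 6.6.2 handles a missing primary endpoint in two stages. Substitution comes first: "It is rare that the primary outcome is missing, but if so, the CDAI response at another visit will be used as the primary outcome". For a patient who stops treatment before visit 7, visit 6 is named as the source. Imputation by chained equations follows "When more than 5% of primary endpoint data is missing under other circumstances".

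On the imputation itself the section says three things that bear on this point:

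- The number of runs is five, and the five analyses are pooled: "Five imputations will be produced and the pooled results of the 5 analyses will be presented".
- The five runs are also to be collapsed into single values: "Imputation will be performed five times and the mean (or median, if a particular variable is not Gaussian) result of imputation will be used to" stand in for the missing values.
- The spread between runs is inspected: "Imputed values will be checked for excessive variability across the five imputation runs assuming data are missing at random (MAR". No threshold and no action are given.

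Convergence and marginal distributions are also to be examined. The section mentions no seed, no Monte Carlo error target and no circumstance in which more than five imputations would be run. Missing questionnaire component scores are to be imputed by the same technique.

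**The concern.** Pooling over a small number of random draws leaves simulation noise in the estimate, its standard error and its degrees of freedom. The trial has one primary test, read at two-sided 0.05 (SAP Sections 6 and 6.1.1). If the result is close to that line, five draws may leave enough noise for the seed to decide the side on which it falls. SAP Section 1 has the primary analysis checked by the Lead Statistician or an independent statistician. A checker who programs it afresh need not obtain the same p-value.

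The variability check does not help. Variation between runs is the quantity that the pooling rule uses to carry missing-data uncertainty into the standard error. Looking for an excess of it, with no definition and no stated response, leaves a judgement open at the time of analysis and does not measure whether five runs are enough.

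**Working it through.** **Inputs from SAP Section 2.3.** The design assumes "a difference in delta CDAI between the two comparison groups of 10, with a Standard Deviation of 14.34", and "90 patients would be needed to detect a significant difference of 10 in delta CDAI with 90% power", that is 45 per group.

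**Reproducing the plan's figure.** A two-sided 5% t-test with 90% power gives 44.2 per group, rounded up to 45. Power at 45 per group is 0.905. The whole-trial total also reproduces: 180/0.90 = 200, or 180/(0.95 × 0.95) = 199.4. The SAP states no figure for Monte Carlo error.

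**Expected test statistic at the design effect.** SE = 14.34 × sqrt(2/45) = 3.02, so t = 10/3.02 = 3.3.

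**Can imputation be triggered?** Section 2.3 says: "If we assume a 5% dropout rate and also account for an expected 5% of patients that have insufficient RNA for the Nano-string analysis". Suppose each of the 90 patients in the primary comparison has a 5% chance of a missing endpoint. More than 5% missing then means 5 or more patients, with binomial probability 0.47. Visit substitution lowers this by an amount that the SAP does not allow one to calculate.

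**Monte Carlo error of the pooled estimate.** Relative to the standard error it is sqrt(FMI/m), where FMI is the fraction of missing information and m the number of imputations. FMI is not in the document; 0.05 to 0.20 is an assumption.

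- FMI 0.05: sqrt(0.05/5) = 0.10
- FMI 0.10: sqrt(0.10/5) = 0.14
- FMI 0.20: sqrt(0.20/5) = 0.20

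A ratio of 5% needs m = FMI/0.05², that is 20, 40 and 80.

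**Effect on a borderline p-value.** Rubin's rules with small-sample degrees of freedom (complete-data df 88), 40,000 simulated seeds per setting, for a dataset whose stable result is t = 2.1 (p about 0.039):

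| FMI | m | 95% range of p over seeds | Seeds with p<0.05 |
|---|---|---|---|
| 0.05 | 5 | 0.024 to 0.065 | 81% |
| 0.05 | 50 | 0.033 to 0.045 | 100% |
| 0.10 | 5 | 0.019 to 0.086 | 69% |
| 0.10 | 50 | 0.031 to 0.049 | 98% |
| 0.20 | 5 | 0.013 to 0.133 | 58% |
| 0.20 | 50 | 0.028 to 0.056 | 90% |

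**Effect away from the line.** At t = 3.3, 99.9% to 100% of seeds with m = 5 stay below 0.05.

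**Whole trials.** 3,000 simulated trials per setting, 45 per group, values missing completely at random, and a correlation of 0.6 with an earlier visit (both assumed):

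| Missing | Two m = 5 seeds disagree, design effect | Type I error, pooled m = 5 | Type I error, mean of five runs filled in |
|---|---|---|---|
| 6% | 2% | 5.1% | 6.2% |
| 10% | 3% | 4.3% | 5.7% |
| 20% | 7% | 4.6% | 8.2% |

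Under the null, two seeds disagree in 1% to 2% of trials. The simulation error of a 5% rate is sqrt(0.05 × 0.95/3000) = 0.4 percentage points. The pooled rates are therefore compatible with 5%, and the mean-fill rate at 20% missing is not.

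**The case against.** Much of the case on the other side stands. Imputation may never be used: the SAP plans 5% dropout, calls a missing primary outcome rare, and substitutes another visit first. If it is used, five imputations lose little efficiency (relative efficiency 0.99, 0.98 and 0.96 at FMI 0.05, 0.10 and 0.20). The p-value ranges above are conditional on a result that is already near 0.05, and they use 88 degrees of freedom from a two-group comparison, not the mixed-effects model of Section 6.1.1. A seed is often set in the analysis code. The figures of 50 imputations and 5% are working thresholds, not derived from the SAP.

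Four stronger readings are tempting, and the document does not support them:

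- *The plan treats between-run variation as a fault.* It does not say so, and it says nothing about rerunning or trimming. What can be said is that the check is undefined and is not tied to adding imputations.
- *That check is the only one made.* Convergence and marginal distributions are examined too, although neither measures Monte Carlo error.
- *Two analysts would commonly reach opposite conclusions.* At the design effect this happens in about 2% to 7% of simulated trials. Section 1 does not say that the checker would use a different seed.
- *Patients last seen early, such as at week 4, would make it much worse.* They have a CDAI at another visit, so they arguably fall under the substitution rule and would not be imputed.

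What remains is that the SAP fixes a number that is too small to settle a borderline result, and closes the route to a larger one.

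**Conclusion.** The point holds as an improvement in precision and reproducibility. Five imputations leave Monte Carlo error of 10% to 20% of the standard error if FMI lies between 0.05 and 0.20, enough for a primary result near 0.05 to depend on the seed. It is not an error of validity: properly pooled, five imputations keep type I error near 5%, and a result of the size that the trial was designed for is practically unaffected. The size rests on the assumed FMI, on imputation being triggered, and on the stable p being borderline. The formula sqrt(FMI/m) applies to the pooled estimate from the planned mixed model as well, but the FMI under that model is unknown.

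A more serious defect sits beside it. Replacing gaps with the mean or median of the five runs is single imputation. It contradicts pooling the separate analyses and discards the between-imputation variance. Under the simulation's assumptions it raises type I error to about 8% at 20% missing. More imputations alone would not cure that.

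**What to change.** In Section 6.6.2:

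1. Replace the fixed five by about 50 imputations, with a seed recorded before database lock.
2. State that the number is raised until the Monte Carlo standard error of the primary estimate is a small fraction of its standard error, for example about 5%. Fifty meets this at FMI 0.10 (sqrt(0.10/50) = 0.045) but not at 0.20 (0.063), where about 80 are needed. Tie the decision to this ratio alone, never to the p-value.
3. Replace the variability check by reporting the Monte Carlo error and the fraction of missing information. Keep the checks of convergence and marginal distributions.
4. Delete the sentence that fills missing values with the mean or median of the runs, so that pooling of the separate analyses is the only method left.
5. Apply the same rule to the questionnaire scores, which borrow this technique.

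The cost is a few sentences in the SAP and some computing time. Design, data collection and sample size are unchanged.

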6.6.3 Handling of outliers

All values will be included in the analyses unless different decisions are made when reviewing the data.

Subject data will not be excluded from the analysis if the subject fails to comply with the visit schedule described in the protocol.

6.7 Statistical analysis issues

6.7.1 Multiple comparisons

The primary and secondary analyses will be carried at 5% significance level. Since one primary endpoint will be analysed, no correction for multiplicity will be applied. Many of the secondary outcome measures are expected to be highly correlated with the primary outcome measure, their analyses will be considered as confirmatory of the primary endpoint. Sub- group analyses are regarded as descriptive and will not be accompanied by formal hypothesis testing.

6.7.2 Multi-centre studies

The key outcome (CDAI) will be summarised using mean and standard deviation by centre.

If there is significant evidence that the centres are different from each other, the variation of centres will be adjusted in the models.

The statistical analyses will be performed using STATA (version 18 or higher). All applied tests will be two sided and p-values of 0.05 will be accepted as statistically significant.

6.7.3 Post-Hoc analysis

Post-hoc analyses may be performed to investigate, where possible, performance of alternative module cut points to inform future research.

7. Safety analysis

Safety analysis will be based on safety population (SAF). Protocol V2.0 section 16 defined the various types of adverse events (AEs). All AEs will be recorded, notified, assessed for seriousness, and severity, reported, analysed and managed in accordance with GCP (see Protocol Section 12.2). The reporting and notification of serious adverse events (SAEs) and of SARs that are related and unexpected, are specified in section 12.2 of the protocol.

AEs, SAEs and/or SARs over the study will be summarised by treatment and biomarker.

8. Additional analysis

8.1 Additional analysis

Adjustments will be made in the analysis for baseline variables that are imbalanced between treatments groups, regardless of the significance of the statistical test.

9. Presentation of analysis

TSC meetings will be carried out every year during the recruitment period of the trial. The Trial Statistician and Trial Manager will produce the open reports. A template of the TSC report is saved in Section 22 of the trial TMF.

The study analyses will take place following database lock and will follow the SAP. The final report will be submitted to the Ethics committee.

References

- 1. Smolen JS, et al., EULAR recommendations for the management of rheumatoid arthritis with synthetic and biological disease-modifying antirheumatic drugs: 2022 update. Ann Rheum Dis. 2023 Jan;82(1):3-18. doi: 10.1136/ard-2022-223356. Epub 2022 Nov 10. Erratum in: Ann Rheum Dis. 2023 Mar;82(3):e76. doi: 10.1136/ard-2022-223356corr1. PMID: 36357155.
- 2. S. Kelly et al., Ann. Rheum. Dis. 74, 611–617 (2015), doi:10.1136/annrheumdis-2013-204603.
- 3. Humby, F. et al. Synovial cellular and molecular signatures stratify clinical response to csDMARD therapy and predict radiographic progression in early rheumatoid arthritis patients. Ann. Rheum. Dis. 78, 761–772 (2019).
- 4. Lewis, M. J. et al. Molecular Portraits of Early Rheumatoid Arthritis Identify Clinical and Treatment Response Phenotypes. Cell Rep. 28, (2019).
- 5. Lliso-Ribera, G. et al. Synovial tissue signatures enhance clinical classification and prognostic/treatment response algorithms in early inflammatory arthritis and predict requirement for subsequent biological therapy: results from the pathobiology of early arthritis cohort (PEA. Ann. Rheum. Dis. 78, 1642–1652 (2019).
- 6. Humby, F. et al. Rituximab versus tocilizumab in anti-TNF inadequate responder patients with rheumatoid arthritis (R4RA): 16-week outcomes of a stratified, biopsy-driven, multicentre, open-label, phase 4 randomised controlled trial. Lancet 397, 305–317 (2021).
- 7. van Riel PL, van Gestel AM. Clinical outcome measures in rheumatoid arthritis. *Ann Rheum Dis.* 2000;59 Suppl 1:i28–i31.

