6.1 Main analyses

6.1.1 Primary endpoint

The primary endpoint of the study will be a continuous outcome of CDAI measure at 16 weeks (visit 7).

The primary analysis will assess the difference in the CDAI comparing the difference in response between the abatacept and placebo groups with the biomarker positive group against the difference in response between the abatacept and placebo groups with the biomarker negative group. This analysis will be on an ITT basis according to original randomisation allocation.

The differences between the groups on the primary outcome will be tested with a mixed-effects model with time as a continuous variable. The CDAI is measured at five time points: (1) Baseline, (2) 4 Weeks, (3) 8 Weeks, (4) 12 Weeks, (5) 16 Weeks. The baseline measurement for the primary outcome is the CDAI score after randomisation. This measurement will be included in the analysis as a covariate.

The mixed-effects model results will be presented as P values and 95% CI. In the mixed-effects model we will use both an 'unstructured' and a '1. order autoregressive' covariance matrix and choose the matrix resulting in the lowest Bayesian information criterion. To assess, if the underlying assumptions behind the mixed-effects model analysis are fulfilled, we will investigate normal quantile plots of residuals, standardized residuals, and random effects. If the underlying assumptions behind the mixed-effects model analysis are clearly violated then we will use a generalized estimation equation for the analysis.

The planned primary analysis is a mixed-effects model adjusted for centre and patient comparing the outcome of CDAI between treatment groups in the biomarker arm (Group 1) and non-biomarker arms (Group 3).

A p-value of less than 0.05 will be taken to indicate statistical significance.

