6.1.2 Secondary analyses

The following secondary endpoints will be reported descriptively within each treatment group:

- 1) Percentage of patients with DAS28(ESR)<3.2 (LDA) at 16 weeks
- 2) Percentage of patients with CDAI ≤10 (LDA) at 16 weeks

- 3) Percentage of patients with CDAI remission at 16 weeks
- 4) Change in HAQ-DI at 16 weeks from baseline
- 5) Change in SF-36 at 16 weeks from baseline

Comparisons by groups will be guided by those performed for the primary endpoint in accordance with the following testing outlined above for the primary analysis:

1 vs 3

1 + 2 vs 3+4

All comparisons involving continuous secondary outcomes will be carried using mixed-effects models comparing treatment groups at 16 weeks, adjusted for baseline score, patient and centre. The associated absolute change difference and 95% confidence interval, as well as the mean change in each group will be reported.

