6.5 Assumptions for analysis

The independence of observations (patients) is assumed within centres, as well as between centres However, the intraclass correlation (ICC) between centres will be tested, if it is significant, a mixed-effects models regression will be used with random effects for centres (and fixed treatment effects).

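### Section 8.1 leaves covariate adjustment to undefined observed imbalance, and the SAP both always adjusts for centre (6.1.1, 6.1.2) and adjusts only after a significant test (6.5, 6.7.2)

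*SAP*

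**What the plan says.** **Covariates.** SAP section 8.1, the only text under the heading for additional analysis, reads: "Adjustments will be made in the analysis for baseline variables that are imbalanced between treatments groups, regardless of the significance of the statistical test". Section 6.1.1 separately fixes baseline CDAI in the primary model ("This measurement will be included in the analysis as a covariate"). Table 1 lists the baseline variables to be summarised, but 8.1 does not refer to it, and no variable is singled out as prognostic.

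**Centre.** Four places deal with it:

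- 6.1.1, primary: "The planned primary analysis is a mixed-effects model adjusted for centre and patient comparing the outcome of CDAI between treatment groups".
- 6.1.2, continuous secondary outcomes: models are "adjusted for baseline score, patient and centre".
- 6.5: "the intraclass correlation (ICC) between centres will be tested, if it is significant, a mixed-effects models regression will be used with random effects for centres".
- 6.7.2: "If there is significant evidence that the centres are different from each other, the variation of centres will be adjusted in the models".

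The first two are unconditional and the last two depend on a test. The SAP does not say which rule prevails.

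**The concern.** An adjustment rule should let two statisticians working apart fit the same model. Section 8.1 makes adjustment mandatory but leaves every operative element open, and it can be applied only once the groups are known. Imbalance is also a poor selection criterion. A variable can be imbalanced and unrelated to CDAI change, or strongly prognostic and balanced; the rule takes in the first and leaves out the second.

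The choice matters more than usual here. Section 2.1 defines the primary contrast as Group 1 against Group 3, that is, biomarker-positive against biomarker-negative patients within abatacept. Baseline differences between those groups need not be chance, so the choice of covariates can change what the contrast estimates.

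On centre, a pre-test that fails to reach significance is not evidence that centres are alike. Following 6.7.2 could remove a term that 6.1.1 says is in the primary model.

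**Working it through.** **1. The plan's own figure.** Section 2.3 takes a difference of 10, SD 14.34 and 90% power; section 6 sets two-sided 0.05. For a two-sample t test with n per group, the noncentrality is (10/14.34)·√(n/2). At n = 44 this is 3.271 and power is 0.899; at n = 45 it is 3.308 and power is 0.905. So 45 per group, 90 in all, is reproduced. Four groups give 180, and 180/0.90 = 200. This is an unadjusted two-mean calculation, so nothing below alters it.

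**2. What 8.1 leaves open.**

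| Needed to apply the rule | Given in 8.1? |
|---|---|
| Candidate variables | No |
| Measure of imbalance | No (only that significance is not the criterion) |
| Threshold | No |
| Groups compared | Treatment groups, undefined; Groups 1 and 3 both receive abatacept |
| Model adjusted | The analysis, unspecified |

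**3. How much the open choice could matter (illustration on assumed inputs).** A simulation used 45 per group, SD 14.34, 20 independent candidate covariates (5 of them correlated 0.25 with the outcome) and 4,000 runs. It compared five options: no adjustment, or adjustment for every variable whose standardised difference exceeds 0.20, 0.25, 0.30 or 0.40.

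- The estimate moved across the five options by a median of about 1.9 CDAI units, against the design difference of 10.
- Whether p fell below 0.05 depended on the option in 7% of runs at a true difference of 0, 29% at 6 and 13% at 10.
- Under no true difference, any single fixed threshold rejected in 3.4% to 3.9% of runs, and no adjustment in 4.5%. Choosing the most favourable of the five gave 8.0%.

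A fixed imbalance rule therefore does not inflate the type I error in this setting. The exposure comes from the rule not being fixed.

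**4. Power of a centre pre-test.** The SAP gives no number of centres or ICC, so both are assumed. With C equal centres of m = N/C patients, a one-way F test at 5% has power P(F > F_crit/R), where R = 1 + m·ICC/(1 − ICC) and F has C − 1 and N − C degrees of freedom. Example for N = 180, C = 10, ICC = 0.02: R = 1 + 18 × 0.02/0.98 = 1.367, F_crit = 1.935, ratio 1.415, power 0.185.

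| ICC | N = 180, C = 10 | N = 180, C = 20 | N = 90, C = 10 | N = 90, C = 20 |
|---|---|---|---|---|
| 0.02 | 0.185 | 0.136 | 0.105 | 0.083 |
| 0.05 | 0.447 | 0.335 | 0.222 | 0.154 |
| 0.10 | 0.757 | 0.674 | 0.447 | 0.318 |

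N = 90 is the size of the Group 1 against Group 3 comparison.

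**The case against.** **Section 8.1 may be supplementary.** It stands under its own heading, apart from 6.1.1 and 6.1.2, which name their model terms. That is a natural reading and cannot be excluded. A reader might infer that the primary model is therefore left unfixed; the text does not establish that. What stands is that 8.1 speaks of the analysis without restriction, neither excludes the primary model nor labels its result a sensitivity analysis, and is mandatory.

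**Avoiding baseline significance tests is sound.** Agreed, but no other criterion replaces them.

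**A count of selected covariates is tempting and not supported.** Table 1 holds about 58 items. At 45 per group, chance puts 24% of variables beyond a standardised difference of 0.25 and 34% beyond 0.20, which suggests 14 to 20 covariates. But 8.1 does not make Table 1 its candidate list, the thresholds are not the SAP's, many items overlap (haemoglobin and haematocrit; weight and BMI), and a chance-only model does not suit biomarker-defined groups. If treatment groups means abatacept against placebo, about 90 each, the proportions fall to 9% and 18%. The count should not be relied on.

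**Inflated type I error** might also be inferred. The simulation shows it only when the most favourable option is picked, and nothing in the SAP says that will be done.

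**The centre conflict may be modest.** If the specific sections govern over the general ones, centre stays in the primary and continuous secondary models, and the pre-tests could be meant for other models, such as the exploratory logistic regressions, which list no centre term. Section 6.5 could also concern only fixed against random effects. But 6.7.2 makes adjustment itself conditional and does not limit which models it covers, so the conflict remains. A flat statement that the pre-test has little power would go too far: at ICC 0.10 with 180 patients it is 0.67 to 0.76.

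**Conclusion.** The point holds as two specification faults in the SAP.

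First, 8.1 is a mandatory adjustment rule that cannot be carried out reproducibly and selects covariates by imbalance rather than prognostic value. The harm is analyst discretion over the reported estimate. Its possible size, about 1.9 CDAI units at the median across five plausible options, depends on the assumed number and strength of covariates and is an illustration, not a prediction.

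Second, the centre rules contradict one another. With 10 to 20 equal centres and 180 patients, the test that 6.5 and 6.7.2 rely on would detect a real centre effect with probability 0.14 to 0.19 at ICC 0.02 and 0.67 to 0.76 at ICC 0.10. It can therefore discard a centre effect that 6.1.1 retains. The number of centres, their equal size and the ICC are assumptions.

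Neither fault affects the sample size or the significance level. Both should be corrected before unblinding.

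**What to change.** - **6.1.1 and 6.1.2:** state that the primary and continuous secondary models contain only the baseline value of the outcome and centre, with patient as the repeated-measures unit, plus any short list of prognostic variables that the sponsor names before unblinding. The SAP identifies no variable as prognostic, so that choice is the sponsor's to justify. Add a note on what adjusting for correlates of the biomarker does to the Group 1 against Group 3 contrast.
- **8.1:** relabel as a sensitivity analysis that does not replace the primary result. State the candidate variables, the imbalance measure and threshold, the groups compared and the model concerned.
- **6.5 and 6.7.2:** delete the significance pre-tests, so that centre is always included as 6.1.1 says, and report the ICC descriptively.

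The cost is SAP wording: no change to sample size, significance level or data collection. The drawback is less freedom to adjust afterwards, which the labelled sensitivity analysis covers.
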